Study category and Rationale	
Risk Category B according to ClinO (Art 2)
 
 Placebo controlled antibiotic treatment with linezolid STADA® authorized in Germany
Clinical Phase:	Phase 3
Background and Rationale:	
Staphylococcus aureus (S. aureus) is the leading bacterial cause of death in high-income countries. Bloodstream infection (bacteraemia) represents a major manifestation of S. aureus affecting 20-30 in 100,000 persons yearly. 90-day mortality rates of 20-30% have remained unchanged over the last decades. Furthermore, S. aureus spreads to secondary body sites in 6-44% of cases, causing long-term impairment in up to a third of survivors, with a relapse rate of 4-10%. While more men are affected by S. aureus bacteraemia (ratio of approximately 1.5:1), women have 18% higher odds of death (OR 1.18) compared to men. So far, more effective treatments have not been identified. Thus, finding better treatments for patients suffering from S. aureus bacteraemia is a high unmet medical need.
 
S. aureus expression of virulence factors facilitates the persistence and spread of the bacteria during infection and causes organ damage. We demonstrated the importance of S. aureus virulence factors in patho-mechanistic analyses directly from infected patient tissue. This led to our hypothesis that patient outcomes could be improved by adding an antibiotic that inhibits virulence factor expression. Several international guidelines recommend this strategy for toxin-mediated infections. However, due to a lack of evidence from randomised trials, this approach has not become standard clinical practice for bacteraemia with S. aureus. Linezolid, an established antibiotic for pneumonia or skin and soft tissue infections, strongly inhibited S. aureus virulence factor expression in preclinical studies.

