3. BACKGROUND AND RATIONALE

3.1 Background and Rationale

Staphylococcus aureus (*S. aureus*) is the leading bacterial cause of death in high-income countries and estimated second leading bacterial cause of death globally after tuberculosis.¹ Bacteraemia (bacteria in the bloodstream) represents a common manifestation of *S. aureus* infection, affecting 20-30 in 100,000 persons annually.²⁻⁴ These numbers have risen in recent years due to aging of the population and other risk factors such as the use of implantable medical devices.^{2-4,6} Approximately 20-30% of patients with *S. aureus* bacteraemia die within 90 days.⁷ This rate has not significantly changed for decades despite active standard antibiotic therapy^{9,10} representing the highest mortality rate among all common bloodstream pathogens.¹ *S. aureus* bacteraemia is reported more often in men than in women.¹¹⁻¹³ Risk factors, as well as diagnostic and therapeutic management can differ between men and women.¹³ Women may experience worse outcomes and higher mortality.^{11,14-16}

In addition, *S. aureus* bacteraemia spreads to secondary body sites in 6-44% of cases,¹⁷⁻²⁰ produces prolonged impairment in up to one-third of survivors,²¹ and is associated with a relapse rate of 4-10%.²²⁻²⁴ Despite the magnitude of disease burden with an estimated 2 million people affected yearly worldwide, less than 3000 patients have been included in published randomised controlled trials (RCTs) testing treatments for *S. aureus* bacteraemia.²⁵ This leaves us with considerable uncertainty about an effective treatment.

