3.8 Justification of choice of study population

A systematic review from 2022 reported that the median age of patients with *S. aureus* bacteraemia ranged from 62 to 72 years⁴. A retrospective observational study looking at cases of *S. aureus* bacteraemia in Switzerland between 2008 and 2021 found that 92% of all *S. aureus* patients were adults². Overall, mortality seems to be lower in children (2-15%)⁹⁰⁻⁹³ suggesting that the disease may manifest differently in children compared to adults. Due to this difference, we will not include children.

In all participating hospitals, infectious disease specialists serving as the local principal investigators, are routinely involved in the care of patients with *S. aureus* bacteraemia. We will approach all patients with *S. aureus* bacteraemia, regardless of sex or gender, who meet the inclusion criteria and do not meet any exclusion criteria about participating in the LIPS trial. Approximately 10-20% of eligible patients will not be able to provide consent themselves due to their compromised health status caused by the *S. aureus* bacteraemia. These patients stand to benefit the most from improved treatment and should not be categorically excluded from trial participation. Therefore, we will include these patients whenever feasible by obtaining consent from a close relative or confirmation by an independent physician not involved in the study. Once the participant's health improves sufficiently to make an informed decision, delayed consent will be sought directly from the participant. We will follow Swissethics guidelines for obtaining consent in emergency situations.⁹⁴

Patients who are pregnant will not be excluded from study participation per se, as linezolid is not formally contraindicated during pregnancy. Limited data exist on the treatment of pregnant women with linezolid, mainly from clinical trials in treating multidrug-resistant tuberculosis. In 31 recorded pregnancies under linezolid exposure in 7 clinical trials, none reported foetal toxicity.⁹⁵ In the event of pregnancy, the treating physician and the patient (or the patient's next of kin) will assess whether the potential benefits outweigh the potential risks to the foetus. As linezolid has been shown to pass into breast milk,^{96 97} breastfeeding should be discontinued prior to and throughout administration of linezolid.

Linezolid is a weak, reversible, and unselective monoamine oxidase inhibitor.⁷⁹ Patients whose background

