7.3 Assignment to study groups

Participants will be allocated 1:1 to either linezolid for 5 days or placebo for 5 days. The randomisation will be stratified by centre and ICU status at time of enrolment and done using block randomisation with varying random block sizes of 2 or 4. The trial statistician will generate the randomisation list outside of the data capture system REDCap®. This list will then be uploaded into the data capture system. The goal is to randomise participants such that the groups are as balanced as possible with respect to study centre and ICU status at time of enrolment.

After informed consent has been obtained and all eligibility criteria have been reviewed and met, the local investigator (or designated staff) enters the minimal required data into REDCap® (i.e., participant ID, year of birth, if participant is on ICU). The allocation is done by REDCap® which will display a unique, randomisation number that remains the same throughout the study. Each randomisation number will correspond to a drug container which is labelled with the unique randomisation number.

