11.4.3 Secondary Analyses

We intend to conduct the following analyses for the secondary outcomes:

Logistic regression

- Returning to usual level of function by day 90
- Microbiological treatment failure 14-90 days after randomisation
- Early microbiological treatment failure 5-13 days after randomisation
- Clinical treatment failure 14-90 days after randomisation
- Persistent bacteraemia defined as positive blood culture on day 5 after randomisation
- Meeting two or more SIRS criteria simultaneously on day 5 after randomisation

Log-normal linear regression

- Length of hospital stay of acute index inpatient hospitalisation (in days)

Poisson regression

- Number of days without being on the Intensive Care Unit (ICU) up to day 90
- Number of days alive and free of antibiotics up to day 90

Cox proportional hazards model

- Time to death up to day 90

Fine & Gray competing risk model

- Time to being discharged alive (assessed until day 90)

The models listed above will include sex, ICU stay at baseline, and centre as adjustment factors (will be further pre-specified in separate data analysis plan).

Wilcoxon-Mann-Whitney test

- Physical health at day 90 as assessed by the short form 36 (SF-36) questionnaire
- Mental health at day 90 as assessed by the short form 36 (SF-36) questionnaire

Subgroup analyses: We will conduct the following subgroup analyses on the primary outcome to assess if treatment effects differ by sex (male vs. female), ICU status at baseline (participants on ICU vs. participants not on ICU), and dominant focus of infection (vascular catheter, skin and soft tissue, endocarditis, osteoarticular, pneumonia, other focus, or focus not identified).

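### The provisional adjustment set for the secondary models names sex, ICU stay and centre but not age, which is recorded for everyone before allocation

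*Protocol*

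**What the plan says.** Section 11.4.3 lists logistic, log-normal, Poisson, Cox and Fine and Gray models for the secondary outcomes. It then states: "The models listed above will include sex, ICU stay at baseline, and centre as adjustment factors". A parenthesis in the same sentence says that this "will be further pre-specified in separate data analysis plan". Section 11.4.1 introduces the whole list as the current intention and expects the detailed plan before the database is closed. The two SF-36 outcomes use an unadjusted rank test and fall outside the sentence.

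Section 7.3 says which data are entered in REDCap to obtain the allocation: "participant ID, year of birth, if participant is on ICU". On design balance it says: "The randomisation will be stratified by centre and ICU status at time of enrolment". Sex and age are both absent from the stratification.

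The protocol motivates its interest in sex. The synopsis reports that "women have 18% higher odds of death (OR 1.18) compared to men", section 3.1 adds "Women may experience worse outcomes and higher mortality", and sex is a named subgroup. On age, section 3.8 gives a median of 62 to 72 years for the disease and contrasts mortality in children with that in adults in order to justify excluding children. It gives no effect of age on death, function or discharge among adults.

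**The concern.** Centre and ICU status belong in the models because they are stratification factors. Sex is not one, so it enters as an additional covariate. The same reasoning would admit age, which is complete by design and, with eligibility open from 18 years upwards, can vary widely.

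The outcomes concerned are those that help explain a win-ratio result: time to death, return to function, length of stay and time to discharge alive. Taken singly, the binary components have little power at the planned effects. A chance age difference between the arms could therefore be of similar size to the effect being looked for, and the named covariates would not correct it directly.

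**Working it through.** **The plan's own figures.** The protocol states no figure for the secondary models. Its sample size, 550 × 1.10 = 605, rounded to an even 606, concerns the win ratio and has no bearing here.

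**Inputs from the protocol (section 11.2 unless stated).** 90-day mortality 22.5% vs 20.3% (mean p = 0.214); worse function 25.0% vs 21.3%; complications 6.3% vs 5.0%; 550 participants before inflation and 303 per arm after it; male:female ratio about 1.5:1 and odds ratio 1.18 for sex (synopsis).

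**Assumptions, not in the protocol.** Age SD 14 years; odds ratio for death 1.3 to 1.6 per 10 years. Per SD this is exp(1.4 × ln 1.3) = 1.44 to exp(1.4 × ln 1.6) = 1.93. The simulations below use 1.3 to 2.5 per SD, which contains that range.

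**1. Share of variance in death explained.** R² ≈ p(1 − p) × Var(linear predictor), with p(1 − p) = 0.214 × 0.786 = 0.168.
- Sex: 0.168 × 0.24 × (ln 1.18)² = 0.0011, about 0.1%.
- Age, low: 0.168 × (1.4 × ln 1.3)² = 0.023.
- Age, high: 0.168 × (1.4 × ln 1.6)² = 0.073.

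These values do not allow for ICU status and centre, so the increment from age would be smaller.

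**2. Chance imbalance with 303 per arm.**
- 95% limit for the difference in mean age: 1.96 × 14 × √(2/303) = 2.2 years.
- Resulting shift in the log odds of death: 0.22 × ln 1.3 = 0.06 to 0.22 × ln 1.6 = 0.10.
- Planned mortality effect: ln[(0.203/0.797)/(0.225/0.775)] = −0.131. The shift is about 45 to 80% of it.
- The same for sex: 1.96 × √(2 × 0.24/303) × ln 1.18 = 0.013, about 10%.

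This is the information of step 1 seen conditionally, not an additional gain.

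**3. Effect in a logistic model.** 4,000 simulated trials per setting, marginal rates held at the protocol's values, with and without age. Mortality used 275 per arm. Function used 195 per arm, which is 275 less about 21% deaths and 10% missing.

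| Outcome, OR per SD | Power without → with age | SE of log OR without → with | Variance ratio, standardised risk difference |
|---|---|---|---|
| Mortality, 1.3 | 9.4% → 9.3% | 0.209 → 0.211 | 0.97 |
| Mortality, 1.6 | 9.1% → 9.4% | 0.209 → 0.213 | 0.95 |
| Mortality, 2.0 | 9.8% → 9.8% | 0.209 → 0.218 | 0.93 |
| Mortality, 2.5 | 9.9% → 10.2% | 0.209 → 0.223 | 0.91 |
| Function, 1.3 | 14.3% → 13.9% | 0.242 → 0.244 | 1.01 |
| Function, 1.6 | 13.8% → 13.9% | 0.242 → 0.248 | 0.96 |
| Function, 2.0 | 14.4% → 15.1% | 0.242 → 0.253 | 0.94 |
| Function, 2.5 | 14.0% → 15.1% | 0.242 → 0.260 | 0.86 |

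The standard error rises slightly. The estimate moves away from the null (mortality at 2.5 per SD: −0.132 to −0.151), because it is now conditional on age. The largest power gain is about 1 percentage point. Section 11.4.3 models death only as time to death by Cox regression. That model was not simulated, and the logistic result stands in for it.

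**4. Log length of stay.** In a linear model the variance factor is 1 − R². For an assumed R² of 0.02 to 0.10 it is 0.98 to 0.90, so 550 participants act like 550/0.98 = 561 to 550/0.90 = 611.

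**5. Sparse outcomes.** Complications of all kinds: 303 × 0.063 + 303 × 0.050 = 34 events. With about 12 centres as fixed effects (assumed), the model has 11 + ICU + sex + treatment = 14 parameters, or 34/14 = 2.4 events per parameter. Each failure outcome at days 14 to 90 is only part of that total.

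**The case against.** The strongest reply is that the protocol does not fix this list. The sentence itself sends the detail to the analysis plan, and covariates for secondary models are commonly settled there. That stands: a reader might infer that age has been ruled out, and the document does not say so. What remains is that these covariates are named, age is not among them, and adding it is a specific change.

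Three further inferences are tempting and should be resisted.
- That the protocol itself shows age to be a strong predictor in this population. Section 3.8 only contrasts children with adults.
- That age gives free precision throughout, for example by turning the 2 to 7% of variance into an equivalent number of extra participants through 1/(1 − R²). That formula belongs to linear models. It does not describe the standard error of a conditional odds or hazard ratio, which rises slightly in the logistic check.
- That sex is a wasted term. It is part of the stated rationale and a named subgroup, and keeping it does not exclude age.

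The objection that an extra term has a cost also stands for the failure outcomes, where events are few for the parameters already planned. It is met by limiting the change to the other outcomes. Finally, the secondary objectives are described as exploratory, which limits what is at stake.

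**Conclusion.** The point holds as a minor efficiency and robustness suggestion. It is not an error or contradiction in the protocol. A complete baseline variable that the randomisation does not balance is missing from a provisional covariate list.

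Under the assumed age effect, an imbalance at the 95% limit would be about 45 to 80% of the planned log odds ratio for death, and adjustment protects against it. Over the simulated range, the power gain for mortality and function is about 1 percentage point at most, so age does not cure their low power. The variance of the standardised risk difference falls by about 3 to 9% for mortality and 0 to 14% for function. For log length of stay it falls by 2 to 10% under the assumed R². All these sizes rest on an age effect that the protocol does not give, and they would be smaller after ICU status and centre. The primary win ratio, the sample size and the type I error are untouched.

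**What to change.** Name age, as a continuous covariate, alongside sex, ICU stay and centre in the models for time to death, return to usual function, length of stay and time to discharge alive. This can be done in section 11.4.3 now or in the analysis plan, in either case before unblinding. Leave age out of the microbiological and clinical failure models, where events are sparse.

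State that the adjusted odds and hazard ratios are then conditional on age as well as on the other covariates. If a marginal effect is wanted for return to function, report the standardised risk difference, which is also where adjustment can reduce variance.

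The cost is one or two sentences and no new data, since year of birth is already collected.

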9. STUDY ASSESSMENTS

9.1 Study flow chart/ table of study procedures and assessments

Study Schedule

	Screening	Enrolment	Intervention phase					In-Hospital Follow-Up (applicable only if participant remains hospitalised)				Close-out
Time point	0-72h before randomisation		Day 1	Day 2	Day 3	Day 4	Day 5	Day 7	Day 14	Day 28	Discharge day	Day 90
S. aureus positive blood culture	X											
Identification of patient		X										
Eligibility checks		X										
Informed consent		X										
Randomisation			X									
IMP administration			X	X	X	X	X					
Time point	0-72h before randomisation		Day 1 (-1 day)	Day 2	Day 3 (±1 day)	Day 4	Day 5 (±1 day)	Day 7 (±1 day)	Day 14 (±3 days)	Day 28 (±4 days)	Discharge day	Day 90 (±7 days)
Clinical assessments												
Baseline data			X ¹									
SIRS criteria								X				
All-cause mortality								Assessed until day 90				
Clinical failure										X	X	X
Length of hospital stay											X	
Length of ICU stay											X	
Antibiotic and/or surgical treatment												X
Laboratory assessments												
Blood cultures				X			X ²					
Creatinine			X				X			X ³		
CRP			X				X					
ALT and gGT			X				X			X ³		
Blood count (Hb, Tc, Lc)			X		X		X	X				
Linezolid trough conc.							X ⁴					
Microbiological failure										X	X	X
New antibiotic resistance												X
Patient reported outcomes												
Quality of life (SF-36)												X
Return to usual level of function												X
Safety assessments												
Serotonin toxicity, myelosuppression, hyperlactataemia ⁵			X	X	X	X	X	X				
Acute kidney injury ⁵							X		X			
C. difficile-associated diarrhoea ⁵												X
SAE / SAR			Collected until day 90									

Abbreviations: S. aureus – *Staphylococcus aureus*; SAE – Severe Adverse Event; SAR – Severe Adverse Reaction; SIRS - Systemic Inflammatory Response Syndrome; ICU – Intensive Care Unit; CRP – C-Reactive Protein; ALT – Alanine Transaminase; gGT – Gamma-glutamyl Transferase; Hb – Haemoglobin; Tc – Thrombocytes; Lc – Leukocytes; SF-36 – Short Form-36

¹ Baseline data include: date of hospital admission, index blood culture, linezolid susceptibility, ethnicity, vital signs, comorbidities, standard antibiotic treatment, markers of severity (mechanical ventilation, cardiac arrest, use of vasopressors, ICU), injection drug use, mental health diagnosis.

² Assessment of persistent bacteraemia. Only required if day 2 blood culture is positive or recorded if done as part of standard of care.

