9.3.4 Assessment of baseline characteristics (day 1)

Most study-specific baseline characteristics are assessed as part of the clinical routine and can be extracted from the patient charts of each centre. The baseline characteristics include date of hospital admission, index blood culture, linezolid susceptibility, ethnicity, vital signs, polymicrobial bacteraemia (defined as more than one organism [at species level] in the index blood cultures, excluding those organisms judged to be contaminants by the treating clinicians), comorbidities, standard antibiotic treatment, markers of severity (mechanical ventilation, cardiac arrest, use of vasopressors, ICU), labour force status, injection drug use, and mental health diagnosis. The data closest to the time before start of the study treatment should be used. The study team of each site will check at the time of randomisation if all relevant information is available from the clinical routine assessment and – if necessary – will add the missing information by contacting the treating team or the participant directly. Together with the participant, the local investigator (or a delegated physician) will assess the level of function 4 weeks before randomisation. In case the participant is not able to provide this information, this data will be assessed at day 90 (asking about their level of function 4 weeks before their *S. aureus* bacteraemia).

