11.2 Determination of Sample Size

We collected retrospective data on the DOOR components from all *S. aureus* bacteraemia patients treated at the University Hospital Basel in 2022 (n=119). Our assumptions for the sample size are based on these data along with what is known from the literature to derive plausible estimates for the DOOR components. Patients who died in the first three days after a *S. aureus* bacteraemia diagnosis were excluded so that we do not overestimate the mortality of the planned trial (of note, most of these patients would probably have died before they could have been included in our study ($n = 8$)). Following extensive consultations with patient representatives, we have established that, for mortality at 90 days, a trial should demonstrate a meaningful relative difference of 10% (equating to an absolute difference of 2.2%). Meanwhile, for the remaining domains, the following relative reductions were deemed acceptable: 15% for level of function and 20% for complications and length of hospital stay).

The sample size was calculated using a simulation approach, for which 1000 synthetic datasets for each combination of plausible values for the relevant parameters were generated. We calculated the p -value of the win ratio for each of the simulated datasets and tested for statistical significance at $\alpha = 0.05$ using the unmatched win-ratio approach described in Pocock et al.¹¹⁷. The final sample size is based on the following specific assumptions:

- The statistical tests are conducted at a two-sided significance level of $\alpha=0.05$, and the desired power is 90%
- The two treatment arms are equal in size (1:1 allocation)
- The proportion of deaths within 90 days in the control group is expected to be 22.5% and 20.3% in the linezolid group (relative reduction of 10%; absolute reduction of 2.2%)
- The proportion of participants with worse level of function in the control group is expected to be 25.0% ²¹, and 21.3% in the linezolid group (relative reduction of 15%; absolute reduction of 3.7%)
- The proportion of participants with any complications (defined DOOR component) will be 6.3% in the control group and 5.0% in the linezolid group (relative reduction of 20%; absolute reduction of 1.3%).

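### The day-5 SIRS model in Section 11.4.3 adjusts for no baseline measure of its own outcome, although the day-1 components are collected; adding the day-1 count would gain a few points of power (low severity)

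*Protocol*

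**What the plan says.** Section 11.4.3 lists six outcomes for logistic regression, among them return to usual level of function by day 90 and two or more SIRS criteria on day 5. For all the regression models it states: "The models listed above will include sex, ICU stay at baseline, and centre as adjustment factors". The sentence then adds that the factors will be specified further in a separate analysis plan, and Section 11.4.1 introduces the analyses as current intentions.

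The baseline data bearing on these two outcomes are:

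- **SIRS.** The footnote to the schedule in Section 9.1 includes vital signs: "Baseline data include: date of hospital admission, index blood culture, linezolid susceptibility, ethnicity, vital signs, comorbidities". Section 9.3.4 lists vital signs and mechanical ventilation and asks for the values closest before the start of study treatment. Section 9.3.6 adds a blood count with leukocytes on the day before or the day of treatment start.
- **Function.** On day 1, together with the participant, "the local investigator (or a delegated physician) will assess the level of function 4 weeks before randomisation". If the participant cannot give this, it is asked at day 90. Section 5.1 defines baseline as the best score in the 4 weeks before randomisation, and success as regaining that score or better.

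**The concern.** Day-5 SIRS is the same construct that can be scored from data taken about four days earlier, so the day-1 count is the obvious candidate for a prognostic covariate. In a logistic model, leaving out a strong predictor costs some power and leaves any chance imbalance in it uncorrected. Sex and centre are unlikely to stand in for it; ICU status may do so in part.

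For function the argument is narrower. The outcome is already scored against the participant's own starting level, but the room to fail still differs by that level. A participant starting at 6 fails with one step down to some limitations. One starting at 3 fails only if hospitalised or in terminal palliative care at day 90. An imbalance in starting level could therefore shift the comparison. Function is the second DOOR domain, and its separate analysis helps to explain the win ratio.

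**Working it through.** **The plan's own figures.** The planned power ("and the desired power is 90" per cent) applies to the win ratio only. The target follows from 550 × 1.10 = 605, or 606 for equal arms (303 each). No power is stated for either secondary model, so there is no figure to reproduce for them.

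**Day-5 SIRS (all rates assumed).** Inputs: 290 per arm (close to 303 × 0.97 = 294), day-5 rates of 40% and 30%, day-1 SIRS in 65%, two-sided 5% test.

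Unadjusted, by formula:

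- SE = √[(0.40 × 0.60 + 0.30 × 0.70)/290] = √(0.45/290) = 0.0394
- z = 0.10/0.0394 = 2.54
- power = Φ(2.54 − 1.96) ≈ 72%

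For the adjusted model, data were simulated from logit P = a + t·(arm) + g·(day-1 SIRS). The values of a and t were solved so that the marginal rates stay at 40% and 30%. Each of 1,500 datasets was fitted with and without the day-1 term.

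| Odds ratio, day 1 to day 5 | Power without | Power with | Arm odds ratio given day 1 |
|---|---|---|---|
| 1 | 73% | 73% | 0.643 |
| 2 | 71% | 73% | 0.636 |
| 4 | 72% | 76% | 0.619 |
| 8 | 72% | 79% | 0.597 |
| 15 | 71% | 79% | 0.578 |

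The simulation error of one entry is about √(0.72 × 0.28/1500) = 1.2 points. A second simulation used the number of criteria, with log-odds of 0.4, 0.7 and 1.0 per criterion and the same 40% and 30%. It gave about 72% to 74%, 71% to 76% and 72% to 81%. The gain is therefore about 2 to 9 points. The tabulated models contained only arm and day-1 SIRS. If ICU status, already in the planned model, carries part of the same information, the real gain is smaller.

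**Return to function (protocol rates).** Control: "The proportion of participants with worse level of function in the control group is expected to be 25.0" per cent. Linezolid: "and 21.3% in the linezolid group (relative reduction of 15%; absolute reduction of 3.7" percentage points.

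- Odds ratio = (0.213/0.787)/(0.250/0.750) = 0.81
- Mortality: "The proportion of deaths within 90 days in the control group is expected to be 22.5% and 20.3% in the linezolid group", so mean survival is 1 − (0.225 + 0.203)/2 = 0.786
- With the 10% missing data assumed in Section 11.2: 303 × 0.786 × 0.90 ≈ 214 per arm
- SE = √[(0.25 × 0.75 + 0.213 × 0.787)/214] = 0.0407
- z = 0.037/0.0407 = 0.91
- power = Φ(0.91 − 1.96) ≈ 15%

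Simulated with a binary baseline covariate (prevalence 50%, assumed), power without and with it was 15% and 15% at a baseline odds ratio of 2, and 15% and 16% at 10. Over all settings run with about 430 survivors it was 12% to 16%. With 303 per arm and an odds ratio of 10 it went from 19% to 21%.

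**Size of the group without a day-1 function score.** Section 2.7 expects 10–20% of patients to be unable to consent. If the same patients cannot rate their function, that is 606 × 0.10 to 0.20 ≈ 61 to 121 participants.

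**The case against.** The strongest objection is that nothing is fixed. The sentence that names the covariates defers their further specification, and covariates for exploratory secondary outcomes are ordinary analysis-plan content. This stands as to severity. It does not remove the point: the protocol names one set for all models, so an outcome-specific baseline will be used only if someone adds it deliberately.

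A reader might infer more than the documents support, in three ways:

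- **That the function model throws away substantial power.** This needs a treatment effect far larger than planned, such as an odds ratio of 0.5. Section 11.2 implies 0.81, where power is about 15% with or without the covariate.
- **That the omitted value largely determines the outcome.** No section links starting function or day-1 SIRS to the result. For function, participants starting low may also be frailer, which could offset their smaller room to fail.
- **That a day-1 function value is missing from the model.** The baseline is a pre-infection score. On day 1 every participant is hospitalised, which is score 2 or lower, so a day-1 status would carry almost no information.

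Two practical objections also stand. No day-1 SIRS count is defined, and Section 9.3.9 says that respiratory rate is usually measured at least daily but that tachypnoea is assessed when clinically indicated, so one component may be incomplete. Adjustment also changes the odds ratio being estimated, as the last column of the table shows. Finally, chance imbalance is a feature of any randomised trial and not a defect of this one; randomisation is stratified by centre and ICU status, and both are in the models.

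**Conclusion.** The point holds as a low-severity improvement. The day-5 SIRS model, as stated, lacks a baseline measure of its outcome that can be built largely from data already collected. Including it would gain about 2 to 9 points of power. This rests on assumed rates of 40% and 30%, an assumed day-1 prevalence or slope per criterion, and little overlap with ICU status. At a moderate association (odds ratio 2 to 4) the gain is 2 to 4 points.

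For return to function the case is protection against chance imbalance only. The protocol's own rates leave that comparison at about 15% power whatever is adjusted for. No figure in the protocol is wrong, and the primary analysis and sample size are unaffected.

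**What to change.** In Section 11.4.3, or in the analysis plan to which it defers:

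1. Add to the day-5 SIRS model the number of SIRS criteria present on day 1, from the last values before the first dose. State in advance, without regard to arm, how a missing respiratory rate is handled.
2. Optionally, add to the return-to-function model the pre-infection level recorded on day 1. Collapse the levels, and use a separate category for not obtained on day 1. A score recalled at day 90 must not enter as a covariate, because it is measured after randomisation.
3. State that the reported odds ratios are conditional on the listed covariates.

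The cost is a sentence or two. The SIRS count entered linearly adds one parameter. The function term adds a few, to a model that already carries about 12 centres, sex and ICU status on roughly 428 × (0.250 + 0.213)/2 ≈ 99 events, which is why the levels should be collapsed. No new data collection is needed if the rule for missing components is in place.
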